#### **2.4.2 Prior, concomitant and post therapies**

Prior medications are defined as treatments taken and stopped prior to first dose of study treatment. Any medication given at least once between the day of first dose of randomized study treatment and the date of the last study visit will be a concomitant medication, including those which were started pre-baseline and continued into the period where study treatment is administered.

Prior and concomitant medications will be listed and summarized in separate tables. Medications will be presented in alphabetical order, by Anatomical Therapeutic Classification (ATC) codes and grouped by anatomical main group. Tables will show the overall number and percentage of patients receiving at least one treatment of a particular ATC code and at least one treatment in a particular anatomical main group. Prohibited medications (listed in Appendix 5.7) will be summarized separately using a frequency summary table, by treatment group.

The number and percentage of subjects receiving systemic therapies for SjS as prior and concomitant background medication will be presented separately by preferred term.

In addition, a descriptive frequency table of the use of DMARDs will be presented separately by DMARDs terms.

### **2.5 Analysis supporting primary objective(s)**

All subjects within the FAS analysis set will be included for the primary analyses.

#### **2.5.1 Primary endpoint**

The ESSDAI score is obtained by summation of the twelve domain scores. Each domain score is obtained by multiplying the activity level with the domain weight. The maximum theoretical ESSDAI score is 123. For details on ESSDAI calculation, please refer to Appendix 5.5.1.

The ESSDAI score will be listed by treatment group, subject and visit/time. Descriptive statistics will be provided by treatment group and visit/time on both raw and change from baseline values.

Spaghetti plots of ESSDAI up to Week 24 will be provided by treatment over time.

#### **2.5.2 Statistical hypothesis, model, and method of analysis**

The change from baseline in ESSDAI is assumed to be normally distributed.

A mixed effect model for repeated measurements (MMRM) will be fitted to the changes from baseline in ESSDAI for all post-baseline time points up to (and including) Week 24 visit including the following fixed factors

- treatment group (LOU064 100 mg *qd*, LOU064 100mg *bid*, placebo)
- visit
- treatment group by visit interaction

- stratification factor using baseline ESSDAI score  $<10$  or  $\geq 10$

and baseline ESSDAI as a continuous covariate. An unstructured variance-covariance matrix will be fitted to model the dependency between repeated observations. Graphical checks on the model assumptions of normality of the data will be provided.

Both unadjusted and adjusted mean values of change from baseline will be presented along with standard error. The difference in the mean change from baseline in ESSDAI at each visit between LOU064 (*qd* and *bid* averaged) and placebo will be estimated from the model and presented together with the associated 95% confidence intervals and one-sided p-value. In addition, the difference in the mean change from baseline in ESSDAI at each visit between LOU064 dosing regimens (*qd* vs *bid*) will be presented along with the associated 95% confidence intervals.

The following two criteria will be used to assess treatment efficacy

- a statistically significant decrease in ESSDAI at Week 24 on LOU064 compared to placebo (at one-sided alpha level at 0.10) and
- an estimated mean change in ESSDAI at Week 24 on LOU064 compared to placebo.

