Eligible subjects will return for the Baseline visit on Day 1. Subjects may reside overnight at the site for logistical reasons, although this would not be considered a hospital admission. Eligibility must be confirmed prior to randomization and required baseline assessments must be completed prior to dosing on Day 1. If preferred by the site for scheduling purposes, some Baseline assessments may be carried out on the evening prior to Day 1.

Treatment

Subjects will be randomized to the respective treatment arms per study part.

Commercially Confidential Information

Subjects will return to the site at approximately 4-weekly intervals, with an additional visit at the end of Week 2 (Day 15). At the study visits, subjects will undergo ESSDAI and ESSPRI assessments as well as other scales/questionnaires, safety and various PK, CCI sample collections as indicated in the Assessment Schedule and described in [Section 8](#). Subjects will be asked to take their morning dose of the study drug at the site on these days. Subjects will return their used drug supply packs for compliance and accountability assessment and will receive a new supply of study drug for the next 4 week treatment period.

Commercially Confidential Information

All study visits will be ambulatory, however, for logistical reasons, it may be necessary for subjects to come to the site the evening before their scheduled assessment visit. In these instances, the subjects may stay overnight at the site, but this would not be considered a hospital admission.

Subjects may be contacted by the Investigator/site staff during the study to ensure compliance/monitor safety by telephone or other means, if it is deemed appropriate or necessary by the Investigator.

Commercially Confidential Information

Follow up and End of Study visit (EoS)

After the last day of dosing, subjects will enter a 30-day follow-up period without study drug treatment. Subjects will then be asked to return to the site at Week 29 for the End-of-Study visit. At this visit, subjects will undergo final assessments as indicated in the Assessment schedule (Table 8-1) Commercially Confidential Information

Upon completion of this visit, subjects will be discharged from the study.

4 Rationale

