8.3.1 EULAR Sjögren's Syndrome Disease Activity Index (ESSDAI)

ESSDAI ([Section 16.4](#)) is a validated disease outcome measure for Sjögren's Syndrome that will be applied to the study subjects. The instrument contains 12 organ-specific domains contributing to disease activity. For each domain, features of disease activity are scored in 3 or 4 levels according to their severity. These scores are then summed across the 12 domains in a weighted manner to provide the total score. The domains (weights) are as follows: constitutional (3), lymphadenopathy (4), glandular (2), articular (2), cutaneous (3), pulmonary (5), renal (5), muscular (6), PNS (5), CNS (5), hematological (2), and biological (1). The maximum possible score is 123.

To calculate ESSDAI, all 12 organ domains must be individually assessed at every scheduled timepoint (from screening visit till end of study). Domain assessments will be entered into a tablet (provided by a central vendor) and ESSDAI score will be calculated by the software. At screening, the ESSDAI subscore from 8 pre-selected domains listed in the inclusion criterion #7, will be calculated to determine patient's eligibility.

For assessments not listed in the protocol as mandatory tests but which may be needed to estimate ESSDAI, including radiography, high resolution computer tomography (HRCT), lung function test (DLCO, FVC), estimated glomerular filtration rate (eGFR), electromyography (EMG), muscle (or any other) biopsy, it is at the investigator's discretion to have these assessed based on the signs and symptoms of the patient so to provide correct ESSDAI readout.

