### 2.6.2 Statistical hypothesis, model, and method of analysis

The change from baseline for ESSPRI, FACIT-F, EQ VAS and PhGA VAS are assumed to be normally distributed.

A mixed effect model for repeated measurements (MMRM) will be fitted, similar to the primary analysis described in Section 2.5.2, to the changes from baseline for each secondary endpoint, for all post-baseline time points up to (and including) Week 24 visit including the following fixed factors

- treatment group (LOU064 100 mg *qd*, LOU064 100mg *bid*, placebo)
- visit
- treatment group by visit interaction
- stratification factor baseline ESSDAI score  $<10$  or  $\geq 10$

and baseline corresponding secondary endpoint fitted, as a continuous covariate. An unstructured variance-covariance matrix will be fitted to model the dependency between repeated observations. Graphical checks on the model assumptions of normality of the data will be provided.

Both unadjusted and adjusted mean values of change from baseline will be presented along with standard error. The difference in the mean change from baseline of each secondary endpoint, at each visit between LOU064 (*qd* and *bid* averaged) and placebo will be estimated from the model and presented together with the associated 95% confidence intervals and one-sided p-value. In addition, the difference in the mean change from baseline of each secondary endpoint, at each visit between LOU064 dosing regimens (*qd* vs *bid*) will be presented along with the associated 95% confidence intervals.

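### Optional gain at almost no cost: let the baseline slope vary by visit in the MMRM, so that the Week 24 contrast is adjusted with its own slope

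*SAP*

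**What the plan says.** SAP 2.5.2 fits changes from baseline at all post-baseline visits up to Week 24. The fixed factors are treatment group, visit, "treatment group by visit interaction" and a "stratification factor using baseline ESSDAI score" cut at 10, followed by "and baseline ESSDAI as a continuous covariate". The only interaction is treatment by visit, so baseline ESSDAI has one slope across visits. On covariance the SAP states: "An unstructured variance-covariance matrix will be fitted to model the dependency between repeated observations". That frees the residual variances and correlations, not the mean slope.

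SAP 2.6.2 repeats the structure for the secondary endpoints: "and baseline corresponding secondary endpoint fitted, as a continuous covariate". Protocol 12.4.2.1 and the data-analysis entry of the protocol summary also list no baseline-by-visit term.

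On visits, the protocol's study design section says "Subjects will return to the site at approximately 4-weekly intervals, with an additional visit at the end of Week 2 (Day 15"), and protocol 8.3.1 requires that "all 12 organ domains must be individually assessed at every scheduled timepoint (from screening visit till end of study"). The schedule gives Weeks 2, 4, 8, 12, 16, 20 and 24: seven visits. The primary test is at Week 24, "at one-sided alpha level at 0.10", on the two regimens averaged against placebo.

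**The concern.** In a model with one baseline slope, generalized least squares (GLS) estimates that slope as a weighted combination of the visit-specific slopes, with more weight on visits with smaller residual variance. If early visits are less variable and change depends more on baseline later, the common slope is too shallow for Week 24, and part of the predictable variation stays in the primary contrast.

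Two things would be at stake: the precision of a comparison with about 24 placebo patients, and the sensitivity of the point estimate to chance baseline imbalance. The second matters because SAP 2.5.2 uses the estimated mean change, as well as the p-value, as an efficacy criterion.

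**Working it through.** **Inputs from the documents.** 72 patients, 24 per arm (SAP 1.1), so 48 versus 24 for the pooled contrast; seven visits; unstructured covariance; one-sided 0.10; stratified randomization (protocol 4.1). The sample-size sections are blacked out, so there is no planned SD, effect or power to reproduce.

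**Assumed inputs.** Week 24 residual SD 5; residual SD at Week 2 of 5, 4 or 2.5, changing linearly; baseline slope constant, or drifting linearly from −0.15 to −0.50 or from −0.10 to −0.60; between-arm baseline imbalance SD 0.8 points (baseline SD 4.5 without stratification would give 4.5 × √(1/48 + 1/24) = 1.125); residual correlation exchangeable at 0.5 or 0.7, or first-order autoregressive at 0.8.

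**Formulas (complete data).** With visit slopes β and residual covariance S, the common slope is b = (1′S⁻¹β)/(1′S⁻¹1). The Week 24 contrast is the difference in mean change minus b times the baseline difference. Its added variance, compared with using the Week 24 slope, is (β₂₄ − b)² × Var(imbalance).

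**Worked example.** Flat SD 5, exchangeable correlation, drift −0.10 to −0.60. All visits have equal weight; the mean visit week is 86/7 = 12.29, a fraction (12.29 − 2)/22 = 0.468 of the drift. So b = −0.10 − 0.50 × 0.468 = −0.334, and the gap is 0.266. Reference variance: 25 × (1/48 + 1/24) = 1.5625 (SE 1.25). Added variance: 0.266² × 0.64 = 0.045, or 2.9%.

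**Range.** The same calculation across the assumptions:

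| Residual SD, Week 2 to Week 24 | Constant slope | −0.15 to −0.50 | −0.10 to −0.60 |
|---|---|---|---|
| Flat at 5 | 0% | about 1% | about 3% |
| 4 to 5 | 0% | 2–5% | 4–10% |
| 2.5 to 5 | 0% | 4–9% | 8–18% |

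Direct simulation of the bottom-right corner gave model SEs of 1.327 (common slope) and 1.250 (by visit): (1.327/1.250)² = 1.127, or 13%. A second, stratified simulation put the SE reduction there at about 7%, or roughly 15% in variance.

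**Power scale.** A test with 80% power at one-sided 0.10 has 1.2816 + 0.8416 = 2.1232. A 3% variance loss gives Φ(2.1232/√1.03 − 1.2816) = 79%; a 15% loss gives Φ(2.1232/√1.15 − 1.2816) = 76%.

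**Validity.** In a separate stratified simulation (72 patients, ESSDAI SD 4, no true effect, correlation with baseline falling from about 0.81 at Week 2 to 0.45 at Week 24; 1,200 trials), the Week 24 slope was about −0.55 and the common slope −0.29. With complete data the mean error was about 0.01 under both models. One-sided rejection was 0.097 (common) and 0.096 (by visit), and model SEs were 0.93 and 0.89.

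**Cost if the slope is constant.** SE 1.245 (common) against 1.249 (by visit): 0.3%. A stratified 72-patient simulation gave 0.2–0.3% with or without about 20% dropout. One smaller run with 24% missing at Week 24 gave 0.899 against 0.904, or 0.6%.

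**The case against.** The strongest reply is that this is a pre-specified, standard model in a randomized trial. A misspecified covariate slope does not bias a randomized comparison with complete data, and stratification on baseline ESSDAI already limits imbalance. All of that stands.

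The premise is also open. The documents give no longitudinal ESSDAI data. Regression to the mean caused by measurement noise appears in full at the first post-baseline visit and gives a constant slope. Eligibility uses the screening ESSDAI, up to six weeks before baseline, so part of any regression may be over before Day 1. This stands too: a growing dependence on baseline is a possibility, not a finding.

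A reader might infer a 13% loss of information, worth 72 × (1 − 1/1.127) = 8 patients. That is the steepest drift combined with a doubling residual SD, and it is a ratio of model SEs. In the simulated drift scenarios the estimate moved by 0.25 to 0.43 points per point of imbalance. That adds 0.25² × 0.64 = 0.04 to 0.43² × 0.64 = 0.12 to a variance of 1.5625, so true sampling variance rises by about 2.6–7.6%, or about 2 to 5 patients. The model SE does drive the test, so some power is lost, but 8 patients is not a fair headline.

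What the reply does not do is supply the missing term. Neither stratification nor the unstructured matrix gives Week 24 its own slope. The blacked-out supplementary analyses would not alter the primary model.

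**Conclusion.** The point holds as a cheap improvement, not as an error. The Week 24 variance loss ranges from 0% (constant slope) to about 15% (steep drift with residual SD doubling; 18% under one assumed correlation). It is typically a few percent. All slopes, SDs and correlations are assumptions.

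A reader might go further and call the Week 24 estimate biased or the test invalid. The documents do not support that: with complete data, mean error was negligible and rejection near 0.10 under both models. Bias appeared only in an assumed stress case, with 24% missing at Week 24 and score-driven dropout in placebo alone, on top of the growing dependence on baseline. There the mean error was −0.23 points with the common slope against −0.02, and rejection was 0.14 against about 0.11. Nothing in the documents suggests that dropout pattern. With a constant slope, the same dropout gave rejection of 0.130 and 0.135 (400 trials), so the raised error rate cannot be put down to the single slope alone.

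The case for the change is the asymmetry: a fraction of a percent if it is not needed, a few percent or more if it is.

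**What to change.** Before unblinding, add a baseline ESSDAI-by-visit interaction to the model in SAP 2.5.2, and each endpoint's own baseline-by-visit interaction in SAP 2.6.2. Leave the other terms, the covariance structure, the contrast and alpha unchanged.

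Bring protocol 12.4.2.1 and the protocol summary into line, or declare the departure in SAP section 4, which now reports no changes. That section needs attention anyway: the protocol model includes geographic region and the SAP model does not.

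The cost is 7 − 1 = 6 extra mean parameters per model and about 0.2–0.3% in the SE if the slope is constant. No new data are needed. The secondary endpoints were not simulated, so extending the change to them rests on the same reasoning, not on a separate result.

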Study treatment	
CCI
 
LOU064 hard gelatin capsules Placebo hard gelatin capsules
 
Commercially Confidential Information

Efficacy assessments	
 • ESSDAI, ESSPRI, FACIT-F, EQ-5D, PhGA
Pharmacodynamic assessments	
 • Commercially Confidential Information
Pharmacokinetic assessments	
 • PK parameters AUC_{tau}, AUC_{0-4h}, C_{max}, T_{max} and MRT and others as needed
Key safety assessments	
 • Adverse event monitoring • Physical examinations • Monitoring of laboratory markers in blood and urine • Central ECG assessment • Additional liver and renal safety monitoring
Other assessments	
Commercially Confidential Information

Data analysis	
Commercially Confidential Information
 
The change from baseline in ESSDAI, ESSPRI, FACIT-F, EQ-5D and PhGA will be analyzed using a MMRM including treatment group, visit, treatment group by visit interaction, stratification factor baseline ESSDAI (<10 or ≥10) and geographic region as fixed factors as well as baseline value of variable analyzed as a covariate. The estimated means per dose and visit and the differences between LOU064 treatment groups and placebo will be derived together with 2-sided 95% confidence intervals.

Key words	
Sjögren's Syndrome, ESSDAI, BTK inhibitor, LOU064, adaptive trial design

1 Introduction

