4.2 Rationale for dose/regimen and duration of treatment

The highest dose planned for this study (100 mg *bid* or *qd*) has demonstrated a maximal effect for LOU064 based on predicted BTK occupancy in blood (B-cell blockade) and tissues, and inhibition of CD63 up-regulation in basophils (IB). This dose is therefore expected to provide maximum clinical effect in tissue, including lymphatic tissue for SjS. In Phase 1, doses up to 600 mg both as single and multiple doses and 200 mg as twice daily dose had been tested in human volunteers and proven to be safe (Section 5.2 in the IB).

Dose/regimen CCI

CCI the dose CCI (100 mg) is tested in a *qd* and in a *bid* regimen and compared to placebo. Due to the covalent nature of the binding of LOU064 to intracellular BTK, the duration of the treatment effect is dependent on the turn-over rate of the BTK molecule.

Commercially Confidential Information

The extent of BTK inhibition required for optimal clinical efficacy still needs to be established. However, it has been hypothesized that 70% inhibition for ~90% of each dosing period at steady state may be appropriate (Herman et al 2018) which would be exceeded clearly by both the *qd*- and *bid* regimen tested in CCI this study. Commercially Confidential Information

Commercially Confidential Information

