12.5.1 Efficacy and/or Pharmacodynamic endpoint(s)

Commercially Confidential Information

Efficacy analysis CCI

The change from baseline over time for secondary efficacy endpoints (ESSDAI, ESSPRI, FACIT-F, EQ-5D and PhGA) will be presented by treatment group and visit. Summary statistics will be presented for original results and mean change from baseline, together with adjusted mean change from baseline and 95% confidence interval estimated from CCI MMRM Commercially Confidential Information. Differences in change from baseline between LOU064 treatment groups and placebo, along with associated 95% confidence intervals, will be presented by visit. Commercially Confidential Information

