### 1.1 Study design

This is a randomized, double-blind, placebo-controlled, multicenter, CCI study to evaluate the safety and efficacy of multiple LOU064 doses in patients with moderate to severe Sjögren's Syndrome (SjS).

Commercially Confidential Information In CCI the study, the CCI dose (100 mg LOU064) is being tested in two different treatment regimen: *qd* and *bid*, and compared to a Placebo arm. A total of approximately 72 subjects will be equally randomized to these three treatment groups for an expected sample size of 24 subjects per group.

[figure not shown]
Commercially Confidential Information

Commercially Confidential Information

Each individual study subject will first undergo a screening prior of up to 6 weeks, a treatment duration of 24 weeks and a follow-up period of approximately 30 days post last administration of study treatment, before the End of Study (EoS) visit. The total duration for each subject in the study, including screening, will be up to 35 weeks, as shown in Figure 1-2.

Figure 1-2: Study flow chart and visit schedule

Key: B: Baseline; R: Randomization; A: Assessments; P: PK sampling; E: end of treatment

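### Does the SAP need to name the qd–placebo and bid–placebo differences as separate outputs?

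*SAP*

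**What the plan says.** SAP 2.5.2 fits a repeated-measures model with a three-level treatment factor, "treatment group (LOU064 100 mg *qd*, LOU064 100mg *bid*, placebo". From it the SAP takes two contrasts at each visit. The first is against placebo: "The difference in the mean change from baseline in ESSDAI at each visit between LOU064 (*qd* and *bid* averaged) and placebo will be estimated", with a 95% confidence interval and a one-sided p-value. The second is qd against bid, with a 95% confidence interval. The same section adds: "Both unadjusted and adjusted mean values of change from baseline will be presented along with standard error".

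SAP 2.6.2 repeats the pattern for the secondary endpoints: "The difference in the mean change from baseline of each secondary endpoint, at each visit between LOU064 (*qd* and *bid* averaged) and placebo", and then qd against bid.

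SAP 1.2.1 defines the summary measure of the primary estimand as LOU064, with qd and bid averaged, against placebo. The efficacy criterion in SAP 2.5.2 is a one-sided test at 0.10 of LOU064 against placebo.

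On the design, Protocol 4.2 says that the 100 mg dose "is tested in a *qd* and in a *bid* regimen and compared to placebo", and SAP 1.1 says that it "is being tested in two different treatment regimen: *qd* and *bid*, and compared to a Placebo arm". Protocol 12.5.1 states: "Differences in change from baseline between LOU064 treatment groups and placebo, along with associated 95% confidence intervals, will be presented by visit". The Data analysis entry of the protocol summary has a similar line: "the differences between LOU064 treatment groups and placebo will be derived together with 2-sided 95% confidence intervals".

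**The concern.** The plural in the two protocol sentences reads most naturally as one difference per active arm. On that reading, the visible SAP gives an interval for the averaged contrast and for qd against bid, but omits the two that compare a single regimen with control. SAP section 4 says that nothing was changed from the protocol, which makes the mismatch look like an oversight.

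What would be at stake is how each regimen is read. If qd and bid differ, the average describes neither of them. The averaged interval cannot stand in for a regimen's own interval, because it is narrower and centred on the mean of the two. A reader interested in one regimen would have to rebuild its interval from other outputs.

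**Working it through.** **Inputs.** SAP 1.1 gives about 72 subjects in three equal groups: 72 / 3 = 24 per group, as the SAP states. The sample-size section is redacted, so no SD, effect size or dropout rate is available. Results are therefore in SD units, with a common SD treated as known. The per-arm numbers below 24, and the unequal arm sizes, are assumptions.

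**1. Are the point differences lost?** Write q, b and p for the adjusted means, A = (q + b)/2 − p for the averaged contrast and D = q − b.

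- A + D/2 = q − p
- A − D/2 = b − p

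Both identities are exact, so the two named contrasts span every treatment comparison in the model.

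**2. How different are the intervals?** The half-width is 1.96 × SE.

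- Averaged contrast, 24 per arm: SE = √(1/48 + 1/24) = √0.0625 = 0.250; half-width 0.490.
- One regimen against placebo: SE = √(1/24 + 1/24) = √0.0833 = 0.289; half-width 0.566.
- Ratio: √(4/3) = 1.155.

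| Contributing per arm | Averaged | One regimen |
|---|---|---|
| 24 | 0.490 | 0.566 |
| 20 (assumed) | 0.537 | 0.620 |
| 16 (assumed) | 0.600 | 0.693 |

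The ratio is the same in every row. It holds for any three-arm design with equal arms and is not particular to this plan.

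**3. Can the regimen-specific interval be rebuilt?** Var(q − p) = Var(A) + Var(D)/4 + Cov(A, D).

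- Equal arms: the covariance is zero, and 0.0625 + 0.0833/4 = 0.0833, which is the direct variance.
- Unequal arms (assumed qd 22, bid 18, placebo 20): dropping the covariance gives SE 0.317, against the correct √(1/22 + 1/20) = 0.309. The missing covariance is 0.5/22 − 0.5/18 = −0.00505.
- The arm-mean standard errors supply most of that correction. With independent arm means, the sum of the two squared standard errors is exact. Covariate adjustment adds only the covariance between adjusted means.

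The effect of that covariance was simulated with 4,000 designs per pattern of arm sizes. The model was a single-visit analysis of covariance with arm, stratum and baseline. Baseline was assumed lognormal (log 9, 0.45) with a floor of 5, and the stratum split at 10. Absolute error in the rebuilt SE:

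| Outputs used | Arm sizes (qd/bid/placebo) | Median | 95th percentile |
|---|---|---|---|
| Arm-mean SEs and both contrast SEs | 24/24/24 | 0.5% | 2.3% |
| Arm-mean SEs and both contrast SEs | 24/16/20 | 0.6% | 2.9% |
| Arm-mean SEs only | 24/24/24 | 1.3% | 7.6% |
| Arm-mean SEs only | 24/16/20 | 1.3% | 8.7% |

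**4. Do the protocol sentences bind this analysis?** Both stand next to redacted text. The protocol summary gives about 252 patients, while this SAP covers about 72, and SAP section 1 refers to a separate interim-analysis SAP and a full-study SAP. The summary speaks of means per dose, but the part described in SAP 1.1 has one dose in two regimens. The model in the summary includes geographic region and the SAP model does not. In Protocol 12.5.1 the subheading and the words around the model name are redacted. These signs do not settle which study part the sentences cover, and a departure from the protocol cannot be read from them.

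**The case for a change.** The best case for a change is that it costs almost nothing: two contrast lines per model already fitted and two table columns, with no new data. An exact model-based interval is better than one rebuilt by the reader, and naming it in advance prevents it from later looking post hoc. Protocol 4.2 and SAP 1.1 both describe two regimens compared with placebo, whatever part the redacted sentences cover.

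The cost argument stands, and so does the observation that the visible text does not name these differences. But neither design statement specifies a contrast: the averaged comparison together with qd against bid satisfies both. The supplementary-analysis sections, SAP 2.5.6 and 2.6.4, are where such contrasts would naturally sit. They are redacted, as is the appendix, so absence from the plan cannot be shown. The reconstruction figures also have limits, since they come from a simplified single-visit model with assumed baselines and not from the planned repeated-measures model.

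The addition has a small cost of its own. Two more unadjusted intervals per visit and endpoint invite reading as tests. If both regimens were tested at one-sided 0.10 with equal arms and a shared placebo (correlation 0.5), the familywise error would be 16.8%. The averaged contrast avoids this and is more precise.

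**Conclusion.** No change is needed. Followed as written, the plan estimates the contrast that its estimand defines and tests it once. Each regimen's point difference follows exactly from the two named contrasts. Its interval, about 15% wider than the averaged one with equal arms, can be closely approximated from the standard errors that the SAP already promises. No estimate, test or decision is affected.

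The conclusion rests on the three-level treatment factor and the reported arm means, both in SAP 2.5.2. The size of the interval difference assumes a common SD and equal arms; the recovery errors depend on the simulation's assumptions. The redactions leave open both whether the regimen-specific differences are listed elsewhere and which study part the protocol sentences govern. Descriptive regimen-specific intervals without p-values, alongside the averaged contrast as the only decision test, would be a convenience for readers and correct no error.
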